Hospitalized patients with comorbid COPD who are at high risk for readmission will be recruited. Specifically patients with comorbid COPD who are to be discharged with (a) admission diagnosis of COPD (GOLD stage II or greater); AND (b) either a prior non-elective hospitalization (one in the past 12 months) OR active smoker. Such participants will undergo questionnaire-based screening for sleep-disordered breathing (STOP-BANG questionnaire) and if they have a high risk for SDB (≥ 3 points) will undergo an overnight portable sleep study for screening prior to hospital discharge (AHI ≥ 10 per hour; $>3\%$ oxygen desaturation for hypopneas). Sites may exercise the option of using the STOP-BANG questionnaire as a screening tool for the purposes of enriching the study population.

Participants who exhibit AHI ≥ 10 per hour; $>3\%$ oxygen desaturation for hypopneas based on the portable sleep test will undergo a PAP “wash in” daytime exposure for 30 minutes after adequate mask-fitting, on the therapy device (AVAPS- AE). Participants who fail to tolerate such therapy, or indicate that they would be unable to use such therapy at night, will not be randomized. Considering the “wash-in” is performed prior to randomization, such participants will not be included as part of the intention to treat (ITT) analysis.

After randomization and prior to discharge, participants will either be initiated on AVAPS-AE therapy (intervention arm) for 60 days or will be referred to the sleep center for further diagnostic testing and therapy initiation (standard of care arm). Participants will complete quality of life questionnaires (Functional outcomes of sleep questionnaire [FOSQ]) at baseline (in-person), and in 30 and 60 days (by mail) post discharge. If participants assigned to the intervention arm are discharged with home O₂ therapy, the O₂ will be entrained into the AVAPS-AE device for nighttime use. At time of hospital discharge, if participants in the intervention arm are not meeting conventional daytime and nighttime criteria for O₂ therapy [(SpO₂ $<88\%$ in room air –day) (> 5 continuous minutes SpO₂ $\leq 88\%$ - nighttime)], they will undergo AVAPS-AE therapy alone.

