Participants who exhibit AHI ≥ 10 per hour; $>3\%$ oxygen desaturation for hypopneas based on the portable sleep test will undergo exposure for 30 minutes after adequate mask-fitting on the therapy device (AVAPS- AE; see device settings under section below entitled, "Standard Procedures and measurements prior to discharge"). Participants who fail to tolerate such therapy, or indicate that they would be unable to use such therapy at night, will not be randomized. Considering the "wash-in" is performed prior to randomization, such participants will not be included as part of the intention to treat (ITT) analysis.

Participants that are placed on PAP therapy during admission and tolerate the therapy will not be subjected to this aspect of the trial. Their experience, during the hospital visit, with the therapy will count as the PAP Wash-In.

Standard Procedures and measurements prior to discharge

Room Air SpO₂ assessment/Supplemental Oxygen

A room air SpO₂ measurement will be used to make a determination if supplemental oxygen is required prior to hospital discharge. SpO₂ should be collected with the participant breathing room air for at least 15 minutes prior. If participants cannot maintain a SpO₂ of at least 90% on room air, supplemental oxygen will be prescribed. If the participant requires supplemental oxygen (according to the guidelines stated

A Pilot, Multi-Center, Randomized, Open-Label, Parallel Group Study to Assess the Effects of a Novel Application of Averaged Volume Assured Pressure Support Ventilation (AVAPS-AE) therapy on Re-hospitalization in Patients with Sleep-Disordered Breathing with co-morbid COPD.

Confidential

below), but was not previously prescribed supplemental oxygen, the study investigator will prescribe it for the participant.

Data collection will consist of key demographic characteristics including gender, age, height, and weight. In addition, a medical history, physical exam, vital signs, medication assessment and Charlson co-morbidity index will all be collected/obtained.

Quality of Life Questionnaires

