Two different quality of life questionnaires will be used in this study. Quality of life questionnaires are important tools for measuring health status changes in participants receiving an intervention. The general health questionnaire that measures functional health, well-being, and physical and mental health (SF-36) will be used in this study. The disease specific quality of life questionnaire (Functional Outcome of Sleep Questionnaire, FOSQ) will also be used in this study. Participants will be asked to complete these questionnaires prior to discharge.

Randomization

Following the completion of the screening procedures to determine study eligibility, participants will be randomly assigned to one of two study arms: 1) Intervention Group (AVAPS-AE), or 2) Standard of Care (SOC). A randomization website will balance the therapy assignments within each of the three classifications of COPD severity: Gold Stage 2, 3, and 4. The research sites will attempt to balance recruitment between stage-3 and stage-4 patients; however, enrollment of stage-2 patients will be capped at 10, as this severity comprises a small proportion of the hospitalized patients with COPD.

Intervention Group:

AVAPS settings:

• Target Tidal Volume	8 ml/kg of ideal body weight
• Pressure Support Min / Max	4 / 26 cmH ₂ O
• Max Pressure	30 cmH ₂ O
• EPAP Min / EPAP Max	4 / 20 cmH ₂ O
• Rate	Auto

Participants in the intervention group will be sent home the AVAPS-AE therapy device. They will receive one on one training on the device as well as a user manual

SOC Group:

A Pilot, Multi-Center, Randomized, Open-Label, Parallel Group Study to Assess the Effects of a Novel Application of Averaged Volume Assured Pressure Support Ventilation (AVAPS-AE) therapy on Re-hospitalization in Patients with Sleep-Disordered Breathing with co-morbid COPD.

Confidential

Standard of care: Portable sleep test results will be communicated to the participant and their health care provider. Timing and determination of further evaluation and treatment of the participant's sleep disordered breathing will be per their participant's health care provider's usual care pathway. Sites with change in usual care pathways that involve immediate initiation of PAP therapy as a standard practice will remain in the study. Such data will be analyzed in "per-protocol analysis". Participants in the SOC arm will receive phone calls to promote medication adherence.

Post Discharge Study period (60 days)

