- One week Device Adherence Assessment (Intervention Group)

During the first 2-7 business days post discharge, research staff will evaluate participant's device adherence via remote download. Participants with poor adherence to AVAPS-AE at home (adequate adherence defined as \geq 4 hours of use on at least 5 of the first 7 nights) will not be included in the "per-protocol analysis" (Such participants will, however, be considered in the intention to treat analysis). Per the investigators discretion, the device setting parameters may be adjusted at this time.

- Weekly Phone Follow-ups (Initial 30 days only):

Phone calls will be made weekly (\pm 2 business days) by the study coordinator to assess mask interface issues (Intervention group) and encourage adherence to AVAPS-AE (Intervention group) and medications (both intervention and SOC group). If participants require an additional visit related to issues noted above, this visit may occur either in the home or as an office to the study site.

- Day 30

At 30 days (\pm 2 business days) post discharge, participants in both Intervention and SOC groups will receive a phone call to determine if they had been admitted to this hospital, or had an unplanned visit to a physician's office or emergency room. Participants will be asked to complete FOSQ and SF-36 questionnaires. Participants will be given the option of completing the questionnaires verbally via phone call or completing handwritten copies and returned via direct mail. Postage paid return envelopes will be provided to participants who elect to complete and return the surveys by mail.

- Day 60

On day 60 (\pm 2 business days), participants in both Intervention and SOC groups will receive a phone call to determine if they had been admitted to this hospital, or had an unplanned visit to a physician's office or emergency room. Participants will be asked to complete a final FOSQ and SF-36 questionnaire. Participants will be given the option of completing the questionnaires verbally via phone call or completing handwritten copies and returned via direct mail. Postage paid return envelopes will be provided to participants who elect to complete and return the surveys by mail. Participants in both

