A Pilot, Multi-Center, Randomized, Open-Label, Parallel Group Study to Assess the Effects of a Novel Application of Averaged Volume Assured Pressure Support Ventilation (AVAPS-AE) therapy on Re-hospitalization in Patients with Sleep-Disordered Breathing with co-morbid COPD.

Confidential

Physical Exam	X		
Medication Assessment	X		
Bedside Spirometry	X		
Room Air SpO2 assesment	X		
Anthropometric measurements	X		
Stop -Bang Questionnaire	X		
20 minute PAP Wash-in	X		
QOL questionnaires (FOSQ and SF-36)	X	X	X
Charleston Co-Morbidity Index	X		
Overnight Portable Sleep Test	X		
Randomization	X		
Device Set up training/Mask fitting	X		
1 week PAP adherence assessment (Treatment Group only)		X	
Weekly phone calls to promote PAP and medication adherence		X	
30 day Healthcare utilization assessment and questionnaire Phone Call		X	
60 day Healthcare utilization assessment and questionnaire Phone call		X	
Transition Plan			X
Optional Registry			X

VII. Statistical Analysis

The method described by Cook and Lawless will be used to handle repeated hospitalizations, physician office visits, or emergency room visits in patients who may or may not also have a terminal event. All repeated hospitalizations that occur in patients will be counted. We will use the count-approach and the gap-time approach, described by Cook and Lawless because we are interested in studying event occurrence rates in the two groups as well as the time to occurrence of events. Analysis will be performed for both 30- and 60-days. Actuarial costs will be assessed in patients belonging to both the intervention and usual care arm. Unadjusted comparisons of these costs will be made by independent t-tests or non-parametric equivalent. Differences will be adjusted for potential confounders and other covariates in

A Pilot, Multi-Center, Randomized, Open-Label, Parallel Group Study to Assess the Effects of a Novel Application of Averaged Volume Assured Pressure Support Ventilation (AVAPS-AE) therapy on Re-hospitalization in Patients with Sleep-Disordered Breathing with co-morbid COPD.

Confidential

multivariate regression models, to include age, gender, race, body mass index, baseline severity of COPD, AVAPS-AE and medication adherence. Biologically plausible effect modification will be evaluated before significant confounders are selected by inspection of significance levels as well as impact of estimated coefficient for hypothesis variable.

Data and Safety Monitoring Plan:

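### Data from sites that adopt immediate PAP are assigned to an undefined per-protocol analysis: read literally, PAP-treated controls enter it, and their ITT status is not stated

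*Combined protocol and SAP*

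**What the plan says.** The SOC Group text (VI. Study Procedures, Randomization) leaves SOC treatment to local practice: "Timing and determination of further evaluation and treatment of the participant's sleep disordered breathing will be per their participant's health care provider's usual care pathway". II. Study Design describes the same arm as participants who "will be referred to the sleep center for further diagnostic testing and therapy initiation (standard of care arm").

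For sites whose practice moves to immediate PAP, the SOC Group text says: "Sites with change in usual care pathways that involve immediate initiation of PAP therapy as a standard practice will remain in the study". The next sentence begins "Such data will be analyzed in" and names the per-protocol analysis. That is the whole rule.

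The One week Device Adherence Assessment uses the same analysis for a different purpose. AVAPS-AE participants who do not reach 4 hours on at least 5 of the first 7 nights are left out of it, with an explicit safeguard: "Such participants will, however, be considered in the intention to treat analysis".

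VII. Statistical Analysis defines neither an ITT nor a per-protocol set, does not say which is primary, and has no rule for PAP use in SOC.

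**The concern.** A per-protocol comparison is normally meant to show the treatment contrast when care goes as planned. Here one rule selects the AVAPS-AE arm for good PAP use, while the other, taken at its word, brings in controls who are also on PAP. The two rules work against each other.

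The protocol states ITT status for wash-in failures (outside, because not randomised) and for poor adherers (inside), but not for participants at immediate-PAP sites. In an open-label trial, a set whose membership is settled after outcomes are known invites a choice driven by results.

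The exposure is also hard to reconstruct. The Study Process Flow lists "1 week PAP adherence assessment (Treatment Group only"), and the Day 30 and Day 60 calls are described as covering admissions, unplanned visits and questionnaires. If PAP starts in SOC are not dated, a small difference is hard to interpret: the device may do little, or the controls may have had similar treatment.

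**Working it through.** **Plan's own figure.** V. Study Enrollment gives 60 completers, 25% attrition and 80 enrolled: 60 / (1 − 0.25) = 80, which reproduces. No alpha, power or effect size is given, so the effect of this rule on the design cannot be computed from the protocol alone.

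**The two rules side by side.**

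| | AVAPS-AE poor adherers | Immediate-PAP sites |
|---|---|---|
| Who is covered | Individuals, by a numeric criterion | Data from the site; whole site, SOC only, or after the change not stated |
| Per-protocol analysis | Left out | Analysed in it |
| ITT | Stated: in | Not stated |

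**How much of SOC could be affected.** V. Study Enrollment caps a site at 25% of total N: 0.25 × 80 = 20, or 0.25 × 60 = 15 if N means completers. With equal allocation (assumed), 20 participants give about 10 of about 40 SOC, or 25%. Randomisation is balanced by GOLD stage and site is not listed, so the split within a site may be uneven.

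**Illustration of lost contrast.** Inputs: 20.5% expected 30-day readmission (VII. Risks and Discomforts). Assumptions not in the protocol: risk ratio RR for AVAPS-AE, a share f of SOC on PAP at once, and full benefit for those controls.

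SOC rate = (1 − f) × 20.5% + f × RR × 20.5%

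Difference = (1 − f) × 20.5% × (1 − RR)

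| RR | f | SOC rate | Difference (points) | Apparent RR |
|---|---|---|---|---|
| 0.50 | 0 | 20.5% | 10.25 | 0.50 |
| 0.50 | 25% | 17.9% | 7.69 | 0.57 |
| 0.50 | 50% | 15.4% | 5.13 | 0.67 |
| 0.60 | 0 | 20.5% | 8.20 | 0.60 |
| 0.60 | 25% | 18.5% | 6.15 | 0.67 |
| 0.60 | 50% | 16.4% | 4.10 | 0.75 |
| 0.70 | 0 | 20.5% | 6.15 | 0.70 |
| 0.70 | 25% | 19.0% | 4.61 | 0.76 |
| 0.70 | 50% | 17.4% | 3.08 | 0.82 |

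At f = 25% the loss runs from 6.15 − 4.61 = 1.54 to 10.25 − 7.69 = 2.56 points. If PAP-treated controls gain only half the benefit, the apparent RR at f = 25% is 0.53 instead of 0.57, or 0.73 instead of 0.76. The 50% rows would need, for example, two sites at the cap with all their SOC participants on PAP.

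For a two-sided 5% comparison of two proportions with 40 per arm, power falls from 24% to 16% (RR 0.50) or from 11% to 8% (RR 0.70) at f = 25%. It is low throughout, as expected in a pilot.

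**The case against.** **PAP in SOC is not crossover.** A reader might infer that these controls broke protocol. They did not: SOC is the provider's usual pathway, and Study Design itself mentions therapy initiation. This stands. It also means the same dilution occurs in the ITT, where it belongs to a comparison with usual care as delivered.

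**Nobody is removed from the ITT.** A reader might infer that the sentence means per-protocol only, so that a site at the cap would take the ITT from 80 to 60. The word only is not in the text, the sites are kept in the study, and a change in pathway may affect only later enrolees. The 80-to-60 reading is not supported. What stands is that ITT membership is left unstated.

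**The sentence may mean exclusion.** The adherence rule uses the per-protocol analysis to leave people out, and the SOC sentence may intend the same. That is possible, but the wording says the data are analysed in that set. Two opposite readings are themselves a reason to fix it.

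**PAP starts may be captured.** II. Study Design and the Day 60 text plan to collect medication changes and procedures from all participants, and also therapies received. It would be wrong to say PAP in SOC goes uncollected. But therapies received are gathered for costing, and no PAP type or start date is specified.

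**In-hospital PAP.** The wash-in text says: "Participants that are placed on PAP therapy during admission and tolerate the therapy will not be subjected to this aspect of the trial". This shows that PAP can precede randomisation. It says nothing about going home on PAP, so it does not show that such controls exist at other sites.

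**Conclusion.** The concern holds as a defect of definition with a predictable direction. The one rule given for immediate-PAP sites leaves its scope open, is silent on the ITT and, taken literally, weakens the contrast in the per-protocol set. The direction toward no difference assumes that PAP benefits controls.

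The size is unknown, because the protocol gives no number of such sites. The 1.5 to 2.6 points at 25% uptake rest on an assumed 30% to 50% relative reduction, full benefit in PAP-treated controls and one site at its cap. They also use 30-day readmission, which is narrower than the primary composite of emergent healthcare use. They illustrate the mechanism and are not an estimate for this trial.

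**What to change.** Replace the analysis sentence in the SOC Group text, and carry the definitions into VII. Statistical Analysis, along these lines:

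- All participants randomised at sites whose usual care changes to immediate PAP are analysed in the ITT in their assigned arm, and the ITT is the primary analysis.
- The per-protocol set is defined for both arms before data review. In SOC it excludes only participants sent home on PAP at the index discharge under an immediate-PAP pathway, at any site. PAP started later, including during or after a readmission, is not a reason for exclusion.
- A sensitivity analysis omits both arms of a site for participants randomised after the date its pathway changed.

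The limit to the index discharge matters. Excluding every SOC participant who starts PAP before day 60 would remove some controls because they were readmitted, which is itself a primary event, and would lower the control event rate artificially. It would also remove controls who simply followed the referral pathway.

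Have each site record its pathway-change date. Add one item to the existing Day 30 and Day 60 calls: any PAP or NIV started outside the study, with type and start date.

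The cost is replacement text, one question on calls already planned, one date per site and one sensitivity analysis. The per-protocol set becomes slightly smaller and remains a non-randomised, supportive comparison. Start dates not collected during follow-up may be impossible to recover later.

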AVAPS-AE is a mode of therapy (Philips Resironics Inc, Monroeville, Pa) with potential advantages over the currently established modes of non-invasive positive pressure ventilation (CPAP and bilevel therapy). This mode of therapy incorporates AVAPS (automated adjustable IPAP setting to maintain target ventilation with a settable rate of change), Auto EPAP and Auto Back up Rate. We believe that these automated parameters will allow better nocturnal ventilatory control to offset the differing elastic and resistive loads imposed by changes in body position during sleep. Furthermore, AVAPS-AE will counter the changing ventilatory requirements due to alterations in lung volumes and airway resistance during different stages of sleep. In summary, the AVAPS-AE mode will enable automatic adjustment in response to ventilatory changes throughout the night. The device platform used in this study with the AVAPS-AE feature is in the BiPAP A40 platform. This device uses existing modes of therapy, therapy features, and algorithms as that which have been previously cleared by the Food and Drug Administration (FDA) (K121623).

III. Study Objectives/Endpoints

Specific aim #1: Evaluate the effects of novel application of Averaged Volume Assured Pressure Support (AVAPS-AE) therapy on time to (# of days) emergent and non-emergent healthcare utilization in patients with sleep-disordered breathing who are hospitalized with co-morbid COPD.

Specific aim #2: Evaluate the effects of novel application of Averaged Volume Assured Pressure Support (AVAPS-AE) therapy on the number of emergent and non-emergent healthcare utilization over 6 months;

A Pilot, Multi-Center, Randomized, Open-Label, Parallel Group Study to Assess the Effects of a Novel Application of Averaged Volume Assured Pressure Support Ventilation (AVAPS-AE) therapy on Re-hospitalization in Patients with Sleep-Disordered Breathing with co-morbid COPD.

Confidential

costs related to re-hospitalization; number of visits to physician offices or emergency rooms, and health-related quality of life (disease-specific and general HR-QOL measures).

Primary Endpoints

Composite end-point of time to occurrence of emergent healthcare utilization (such as re-hospitalization, unscheduled physician office visits, urgent care visits or emergency room visits).

Secondary Endpoints:

1. Healthcare Costs
2. Change in quality of life (SF-36) at 30 and 60-days
3. Change in quality of life (FOSQ) at 30 and 60-days

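### Per-protocol membership depends on week-one device use in the AVAPS-AE arm only, so an early readmission can drop a participant and a primary event from that arm while SOC keeps the same event

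*Combined protocol and SAP*

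**What the plan says.** The rule is in Section VI, One week Device Adherence Assessment. It concerns "Participants with poor adherence to AVAPS-AE at home" and defines adequate adherence in brackets: those without at least 4 "hours of use on at least 5 of the first 7 nights) will not be included in the" per-protocol analysis. The next sentence protects the main comparison: "Such participants will, however, be considered in the intention to treat analysis". On timing: "During the first 2-7 business days post discharge, research staff will evaluate" adherence by remote download.

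The check belongs to one arm. The Study Process Flow table lists it as "1 week PAP adherence assessment (Treatment Group only)". The only per-protocol statement about SOC is in Section VI, SOC Group: sites whose usual care moves to immediate PAP stay in the study, and their data go to the per-protocol analysis. That removes no SOC participant for anything that happens in week one.

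The primary endpoint in Section III is a "Composite end-point of time to occurrence of emergent healthcare utilization (such as re-hospitalization" and other unplanned contacts). Section VII, Statistical Analysis, says "We will use the count-approach and the gap-time approach" and "Analysis will be performed for both 30- and 60-days". It names no analysis set, does not rank ITT and per-protocol, and does not say how a night in hospital counts towards the seven.

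**The concern.** Membership of one arm is decided after randomisation, inside the outcome window, by a measurement that the outcome can alter. A participant readmitted early is away from the home device. If those nights score as non-use, the readmission causes the exclusion, and the event leaves the AVAPS-AE numerator. An SOC participant with the same readmission stays in and is counted.

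The result is a per-protocol contrast that leans towards AVAPS-AE when the treatment does nothing. The lean is larger at 30 days than at 60, because week one is a larger share of the shorter follow-up. In an open-label pilot this size, an unwritten rule on hospital nights could also be settled after outcomes are known.

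**Working it through.** **Inputs from the protocol.** 20.5% expected 30-day readmission (Section VII, Risks and Discomforts); up to 80 enrolled for 60 completers at 25% attrition (Section V); five of seven nights required (Section VI); horizons of 30 and 60 days (Section VII). The enrolment figure reproduces: 60 / (1 − 0.25) = 80. No power, alpha or effect size is stated.

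**Assumptions not in the protocol.** Constant hazard; 1:1 allocation; no true treatment effect; hospital nights counted as non-use; length of stay; home non-use rate; share of composite events that are admissions. Forty per arm is a maximum, because wash-in failures are not randomised.

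**Step 1, hazard.** h = −ln(1 − 0.205) / 30 = 0.00765 per day. With P(t) = 1 − exp(−ht): 3.75% have an event by day 5, 5.21% by day 7, 20.5% by day 30 and 36.8% by day 60.

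**Step 2, who is excluded.** An admission on night j lasting L nights loses min(L, 8 − j) of the seven. The rule tolerates two lost nights. With perfect home use, exclusion therefore needs j ≤ 5 and L ≥ 3. With missed home nights, shorter or later stays can also exclude.

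**Step 3, closed-form check (risk ratio).** If every event by day 5 is such an admission, the AVAPS-AE per-protocol risk is (P(T) − P(5)) / (1 − P(5)).
- 30 days: (0.205 − 0.0375) / 0.9625 = 0.174, and 0.174 / 0.205 = 0.85.
- 60 days: (0.368 − 0.0375) / 0.9625 = 0.343, and 0.343 / 0.368 = 0.93.

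**Step 4, first-event Cox hazard ratio.** Null simulation with at least 1,000,000 per arm; exclusion applied to AVAPS-AE only.

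| Scenario | 60 d | 30 d |
|---|---|---|
| Every event an admission of 3+ nights, perfect home use | 0.90 | 0.82 |
| 55% of events are such admissions | about 0.95 | 0.90 |
| 25% are | 0.97 | 0.95 |
| 2-night stays, perfect home use | 1.00 | 1.00 |
| 2-night stays, 10% home non-use per night | 0.95 | 0.91 |
| 2-night stays, 20% home non-use | 0.92 | 0.86 |
| 3-night stays, 20% home non-use | 0.88 | 0.79 |
| 20.5% is readmissions only and 55% of the composite; perfect home use | 0.94 | 0.89 |

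The last row uses h / 0.55 = 0.01390 per day. Rows with a stated stay length treat every event as an admission.

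**Step 5, event counts.** With f the share of events that are 3+ night admissions and perfect home use, the rate ratio is (60 − 5f) / 60 at 60 days and (30 − 5f) / 30 at 30 days: 0.92 / 0.83 for f = 1 and 0.95 / 0.91 for f = 0.55.

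**Step 6, participants.** 40 × 0.0375 = 1.5 if all are otherwise adherent and f = 1. With f = 0.55 it is 0.83; with 60% otherwise adherent, 0.9; with both, 0.5.

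**Step 7, against sampling error.** Take 40 SOC and 24 AVAPS-AE (60% adherent) in the per-protocol set. The standard error of the log hazard ratio is √(1/14.7 + 1/8.8) = 0.43 at 60 days and √(1/8.2 + 1/4.9) = 0.57 at 30 days. Biases of ln 0.90 = −0.11 and ln 0.82 = −0.20 are about a quarter and a third of these. For 0.88 / 0.79 (−0.13 and −0.24) they are about 0.3 and 0.4.

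**Step 8, remedies under the same null.** A day-7 landmark in both arms gives 1.00 at both horizons, with or without home non-use, if adherers and non-adherers share the same prognosis. Without a landmark, treating hospital nights as neutral gives 1.00 with perfect home use. At 20% home non-use it gives up to about 1.02 / 1.03 if hospital nights are credited as used. If five-sevenths of home nights is required, rounded up, 2-night stays give 0.98 / 0.96.

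**The case against.** The strongest reply is textual. The rule speaks of adherence at home, so nights in hospital may never have been meant to count, and the mechanism then largely disappears. This stands as a possible reading. Against it, the criterion is fixed at seven nights with no provision for nights away, and a download from a device left at home would show no use.

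The second reply is scale: about one participant, well under one standard error, in a pilot whose ITT analysis keeps everyone. That stands too, and it limits the weight of the point.

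Third, the landmark discards early events and does not cure selection of healthier participants by adherence. Both are true, and the fix must say so.

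Some stronger readings are tempting and not supported:
- A reader might infer that the trial's main result is biased. Section VI keeps these participants in ITT, and nothing makes per-protocol primary.
- A reader might infer that every week-one admission is dropped. Only those leaving fewer than five adherent nights are.
- A reader might take 0.90 / 0.82 as a worst case, or take short stays as harmless. Neither holds once home nights are missed.
- A reader might infer that the criterion cannot be judged, because the download may be done on business day 2, when only two to four nights have passed. The window runs to business day 7, seven nights are available by business day 5 or 6, and nothing says classification is locked at the earliest download. This timing point is minor.

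**Conclusion.** The point holds as a defect in the per-protocol definition, conditional on hospital nights counting as non-use. It is one-sided: under that reading and no true effect, every scenario that excludes anyone favours AVAPS-AE. The null hazard ratio at 60 / 30 days runs from 1.00 / 1.00 to 0.88 / 0.79 over the scenarios tried, and none of these is a strict upper bound. The figures rest on the constant hazard, the assumed allocation, stay lengths and home use, and on applying the 20.5% readmission rate to the composite.

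It deserves correction because it is systematic and cheap to remove, not because it threatens the main analysis. Separately, selecting adherers in one arm only is a further source of bias. The documents give no basis for sizing it.

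**What to change.** In Section VI (adherence assessment) and Section VII (Statistical Analysis):

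1. Restrict the per-protocol comparison, in both arms, to participants event-free through night 7. Start the clock and the recurrent-event counts at day 7. End follow-up at days 30 and 60 after discharge, so that the scheduled calls still cover it.
2. Classify adherence only from a download covering all seven nights; the existing window allows this. State how hospital nights count.
3. Name ITT as the primary analysis and per-protocol as supportive, and state that selection by adherence remains.

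**Cost.** Wording only; the data are already collected. The supportive analysis omits about 5% of patients, 5.21 / 36.8 = 14% of 60-day first events and 5.21 / 20.5 = 25% of 30-day first events. If readmissions are only 55% of the composite (assumption), it omits 9.3% of patients and 16% and 27% of first events.

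**Alternative that keeps early events.** State that hospital nights are not non-use and judge adherence on home nights only. This removes the one-arm exclusion with perfect home use and otherwise leaves the null hazard ratio within about 0.03 to 0.04 of 1.00, depending on how the five-of-seven threshold is scaled. That scaling must be written down, and the readmitted participants are then classified on fewer nights.
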